### 8.3.3 CLASSIFICATION OF AN ADVERSE EVENT

#### 8.3.3.1 SEVERITY OF EVENT

The following guidelines will be used to describe the severity of AEs.

- **Mild** – Events require minimal or no treatment and do not interfere with the participant's daily activities.
- **Moderate** – Events result in a low level of inconvenience or concern with the therapeutic measures. Moderate events may cause some interference with functioning.
- **Severe** – Events interrupt a participant's usual daily activity and may require systemic drug therapy or other treatment. Severe events are usually potentially life-threatening or incapacitating.

Of note, the term "severe" does not necessarily equate to "serious." Severity is a measurement of intensity. Thus, a severe reaction is not necessarily a SAE. For example, a headache may be severe in intensity, but would not be serious unless it met one or more of the criteria for a serious adverse event.

#### 8.3.3.2 RELATIONSHIP TO STUDY TREATMENT

All AEs must have their relationship to study treatment assessed by the clinician who examines and evaluates the participant based on temporal relationship and his/her clinical judgment. The degree of certainty about causality will be graded using the categories below. In a clinical trial, the study product must always be suspect.

- **Definitely Related** – Evidence indicates a reasonable temporal sequence of the event with the study drug administration exists or that the association of the event with study drug administration is unknown and the event is not reasonably supported by other conditions such that:
  - There is a clinically plausible time sequence between onset of the AE and study treatment administration, and/or
  - There is a biologically plausible mechanism for study treatment causing or contributing to the AE, and
  - The AE cannot be reasonably attributed to concurrent/underlying illness, other drugs or procedures.
- **Potentially Related** – Evidence indicates a possible relationship to the study drug such that:

- The event occurs within a reasonable period of time relative to the treatment that makes a causal relationship possible, but plausible explanations may also be provided by other causes such as other drugs, products, chemicals, underlying disease, environment, etc.
- The event is possibly related to the study treatment.
- **Not Related** – Evidence indicates no plausible direct relationship to the study drug such that:
  - A clinically plausible temporal sequence is inconsistent with the onset of the AE and drug administration, and/or
  - A causal relationship is considered biologically implausible
  - The AE can be attributed to concurrent/underlying illness, other drugs or procedures.

#### 8.3.3.3 EXPECTEDNESS

The investigator will be responsible for determining whether an AE is expected or unexpected. An AE will be considered unexpected if the nature, severity, or frequency of the event is not consistent with the risk information previously described for the study treatment. Expectedness should be determined if the AE is characterized as related to treatment and is serious (met one or more of the criteria for an SAE).

#### 8.3.3.4 OUTCOME

The clinical outcome of an AE will be characterized as follows:

- Resolved without sequelae
- Resolved with sequelae (specify)
- Death
- Ongoing (i.e., continuing at time of study discontinuation)
- Unknown

#### 8.3.3.5 TREATMENT OR ACTION TAKEN

The clinical treatment or action taken from an AE will be characterized as follows:

- None
- Medical intervention
- Surgical intervention
- Unknown
- Other (specify)

#### 8.3.3.6 ACTION TAKEN WITH INVESTIGATIONAL PRODUCT

The action taken with the IP will be characterized as follows:

- None
- Drug temporarily withdrawn
- Drug discontinued
- Unknown

#### 8.3.4 TIME PERIOD AND FREQUENCY FOR EVENT ASSESSMENT AND FOLLOW-UP

The occurrence of an AE or SAE may come to the attention of study personnel during study visits and interviews of a study participant presenting for medical care, or upon review by a study monitor. At study visits, study personnel should pose general questions to the participant to ascertain if the participant experienced any issues prior to the visit.

All AEs, including local and systemic reactions not meeting the criteria for SAEs, will be captured on the appropriate eCRF. Information to be collected includes event description, date of onset, clinician's assessment of severity, relationship to study product (assessed only by those with the training and authority to make a diagnosis), and date of resolution/stabilization of the event. All AEs occurring while in the study must be documented appropriately regardless of relationship.

Any medical condition that is present at the time that the participant is screened will be considered as Baseline and not reported as an AE. However, if the study participant's condition deteriorates at any time during the study, it will be recorded as an AE.

Changes in the severity of an AE will be documented to allow an assessment of the duration of the event at each level of severity to be performed.

The investigator or designee will record all reportable events with start dates occurring any time after study drug is first administered until 7 (for non-serious AEs) or 30 days (for SAEs) after the last day of study participation. At each study visit, the investigator will inquire about the occurrence of AE/SAEs since the last visit. Events will be followed for outcome information until resolution or stabilization.

Whenever possible, recognized medical terms should be used when recording AEs. Colloquialisms and/or abbreviations should not be used. Only one medical concept, preferably a diagnosis instead of individual symptoms, should be recorded as the event (e.g., record congestive heart failure rather than dyspnea, rales and cyanosis). However, if a constellation of signs and/or symptoms cannot be medically characterized as a single diagnosis or syndrome at the time of reporting, each individual sign or symptom should be recorded as a separate AE. A diagnosis that is subsequently established should be reported as follow-up information.

Adverse events occurring secondary to other events (e.g., sequelae) should be identified by the primary cause. A "primary" event, if clearly identifiable, should represent the most accurate clinical term to record as the AE event term. For example: Orthostatic hypotension  $\Rightarrow$  fainting and fall to floor  $\Rightarrow$  head trauma  $\Rightarrow$  neck pain. The primary event is orthostatic hypotension and the sequelae are head trauma and neck pain.

Centralized safety oversight for this multi-site study will be provided by the Medical Monitor.

#### 8.3.5 ADVERSE EVENT REPORTING

The investigator must record nonserious adverse events and submit on the eCRF in a timely manner.

### 8.3.6 SERIOUS ADVERSE EVENT REPORTING

The study clinician will immediately report to the sponsor and Medical Monitor any SAE, whether or not considered study treatment-related, including those listed in the protocol or investigator brochure and must include an assessment of whether there is a reasonable possibility that the study treatment caused the event [21 CFR 312.64(b)]. Serious adverse events must be reported immediately to the below listed individuals using the Serious Adverse Event Report (SAER) form. Sites will also be instructed to document the event in the Serious Adverse Event eCRF.

[REDACTED]	[REDACTED]

All SAEs will be followed until satisfactory resolution or until the site investigator deems the event to be chronic or the participant is stable. Other supporting documentation of the event may be requested by the study sponsor and should be provided as soon as possible.

The study sponsor or designee will be responsible for notifying the Food and Drug Administration (FDA) of any unexpected fatal or life-threatening suspected adverse reaction as soon as possible, but in no case later than 7 calendar days after the sponsor's initial receipt of the information [21 CFR 312.32(c)(2)]. In addition, the sponsor must notify the FDA and all participating investigators in an Investigational New Drug (IND) safety report of potential serious risks, from clinical trials or any other source, as soon as possible, but in no case later than 15 calendar days after the sponsor determines that the information qualifies for reporting [21 CFR 312.32(c)(1)]. In each IND safety report, the sponsor must identify all IND safety reports previously submitted to the FDA concerning a similar suspected adverse reaction and must analyze the significance of the suspected adverse reaction in light of previous, similar reports or any other relevant information. The sponsor must report any suspected adverse reaction that is both serious and unexpected. The sponsor must report an AE as a suspected adverse reaction only if there is evidence to suggest a causal relationship between the drug and the AE.

### 8.3.7 REPORTING EVENTS TO PARTICIPANTS

It will be the responsibility of the principal investigator to inform participants of any AEs or SAEs deemed related to the study drug and of any study-related results.

### 8.3.8 EVENTS OF SPECIAL INTEREST

Not applicable.

### 8.3.9 REPORTING OF PREGNANCY

Women of Childbearing Potential (WOCBP) includes any females who have experienced menarche and who have not undergone successful surgical sterilization (hysterectomy, bilateral tubal ligation or bilateral oophorectomy) or are not postmenopausal at least 12 months since last menses. WOCBP will be required to use designated methods of birth control during the course of the study. All women who are pregnant, nursing an infant or planning a pregnancy during the duration of this study will be excluded from participation.

If a participant or investigator suspects that the participant may be pregnant prior to study drug administration, the study drug should be withheld until the results of pregnancy testing are available. If pregnancy is confirmed, the participant should not administer the study drug and should not be enrolled in the study.

[figure not shown]
If a female participant becomes pregnant during the study, use of the study drug should be discontinued immediately. The investigator will notify the sponsor (or designee) immediately after the pregnancy is confirmed. The investigator will (1) obtain a consent from the female participant for pregnancy follow-up and (2) follow the progress of the pregnancy to term. The investigator should document the outcome of the pregnancy and provide a copy of the documentation to the sponsor or designee. The sponsor or sponsor's designee will be responsible for reporting to the IRB and regulatory agencies as appropriate.

## 9 STATISTICAL CONSIDERATIONS

### 9.1 STATISTICAL HYPOTHESES

This study is designed to demonstrate the superiority of TP-03 to vehicle control.

- Population: Participants with *Demodex* blepharitis as defined by the enrollment criteria
- Primary Efficacy Endpoint: Cure based on a collarette score of 0 for the upper eyelid of the analysis eye at Day 43
- Secondary Efficacy Endpoints:
  - *Demodex* mite eradication (mite density of 0 mites/lash) from the analysis eye at Day 43
  - Composite cure based on collarette score (0) and erythema score (0) for the upper eyelid of the analysis eye at Day 43
  - Erythema cure based on erythema score (0) for the upper eyelid of the analysis eye at Day 43
- [REDACTED]
  - [REDACTED]
  - [REDACTED]
  - [REDACTED]

- Hypotheses:

*The primary efficacy hypothesis is:*

$H_{01}$ : The proportion of participants cured at Day 43, based on a collarette score of 0 for the upper eyelid of the analysis eye, by treatment with TP-03, 0.25%, is  $\leq$  the proportion cured by treatment with vehicle.

$H_{11}$ : The proportion of participants cured at Day 43, based on a collarette score of 0 for the upper eyelid of the analysis eye, by treatment with TP-03, 0.25%, is  $>$  the proportion cured by treatment with vehicle.

*The secondary efficacy hypotheses are:*

#### Demodex Eradication

$H_{02}$ : The proportion of participants with *Demodex* eradicated at Day 43 (mite density of 0 mites/lash) in the analysis eye by treatment with TP-03, 0.25%, is  $\leq$  the proportion with *Demodex* eradicated by treatment with vehicle.

$H_{12}$ : The proportion of participants with *Demodex* eradicated at Day 43 (mite density of 0 mites/lash) in the analysis eye by treatment with TP-03, 0.25%, is  $>$  the proportion with *Demodex* eradicated by treatment with vehicle.

#### Composite of Collarette and Erythema Cure

$H_{03}$ : The proportion of participants with a composite cure, collarette score of 0 and erythema score of 0, for the upper eyelid of the analysis eye at Day 43 by treatment with TP-03, 0.25%, is  $\leq$  the proportion with a composite cure by treatment with vehicle.

$H_{13}$ : The proportion of participants with a composite cure, collarette score of 0 and erythema score of 0, for the upper eyelid of the analysis eye at Day 43 by treatment with TP-03, 0.25%, is  $>$  the proportion with a composite cure by treatment with vehicle.

#### Erythema Cure

$H_{04}$ : The proportion of participants with an erythema cure, score of 0, for the upper eyelid of the analysis eye at Day 43 by treatment with TP-03, 0.25%, is  $\leq$  the proportion with an erythema cure by treatment with vehicle.

$H_{14}$ : The proportion of participants with an erythema cure, score of 0, for the upper eyelid of the analysis eye at Day 43 by treatment with TP-03, 0.25%, is  $>$  the proportion with an erythema cure by treatment with vehicle.

## 9.2 SAMPLE SIZE DETERMINATION

A total sample size of 300 subjects (150 subjects per arm) yields approximately 99% power to establish superiority of TP-03 to vehicle in the participants meeting the primary efficacy endpoint assuming a response rate of 80.0% in TP-03 and 15.8% for vehicle treatments, respectively using Pearson chi-squared to test a 1-sided hypothesis with a significance level of 0.025. Response rates for sample size calculations are based upon a prior OUS clinical study of TP-03, 0.25%, for the treatment of *Demodex* blepharitis.

Based on the results of a more recent Phase 2b/3 study, TRS-009 (Saturn-1), with a response rate of 44.0% for the TP-03 treatment group and 7.4% for the vehicle treatment group, a total sample size of 300 subjects still provides greater than 99% power.

The study will be considered a success and TP-03, 0.25%, will be considered superior to vehicle in clinical cure if  $H_0$  is rejected in favor of  $H_1$ . With this sample size, the study will have > 95% power to claim success for clinical cure. A closed hierarchical testing structure will be used such that the analysis will first be performed for the primary efficacy endpoint. [REDACTED]

Accounting for a 30% discontinuation, approximately 209 subjects per arm (approximately 418 total) will be randomized. The planned enrollment is much greater than typically planned to achieve 300

completed subjects due to concerns regarding the impact of COVID-19 and the possibility that up to two sites are unable to complete the study.

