**Secondary Endpoints:**

- *Demodex* mite eradication (mite density of 0 mites/lash) from the analysis eye at Day 43.
- Composite cure based on collarette score (0) and erythema score (0) for the upper eyelid of the analysis eye at Day 43.
- Erythema cure based on erythema score (0) for the upper eyelid of the analysis eye at Day 43

Safety will be determined by assessing adverse effects related to the active treatment [REDACTED]

[REDACTED]

**Phase:** 3

**Number of Participants:** Up to 418 participants will be enrolled [REDACTED]

[REDACTED]

**Study Population:** Participants with blepharitis due to *Demodex* infestation defined as having an elevated mite density, collarettes and erythema

**Description of Sites:** Up to 25 sites in the United States

**Description of Study Treatment:** Participants eligible to be randomized will receive one of the following treatments administered bilaterally BID for 43 days: TP-03, 0.25%, or TP-03 vehicle

**Study Duration:** Approximately six months

**Participant Duration:** The study duration for an individual participant is estimated to be approximately three months

**Summary of Visit Schedule:** Screening, Day 1, Day 8, Day 15, Day 22, Day 43, Day 57 [REDACTED] and Day 90. The Day 90 visit should only be conducted at sites that performed specular microscopy.

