## 4 STUDY DESIGN

### 4.1 OVERALL DESIGN

The Phase 3 study is a randomized, controlled, multicenter, double-masked, parallel trial to evaluate the safety and efficacy of TP-03, 0.25%, for the treatment of *Demodex* blepharitis. The primary objective of the study is to demonstrate the safety and efficacy of TP-03, 0.25%, compared to its vehicle for the treatment of mild to severe *Demodex* blepharitis. The primary efficacy endpoint will be cure based upon collarettes as evaluated by the study grading scale (see Appendix A: Collarette Grading). Safety will be determined by assessing adverse effects related to the active treatment [REDACTED]

[REDACTED]

[REDACTED]

The sample size is planned to be a minimum of 300 participants. The plan is to enroll up to 418 subjects in a 1:1 ratio of active: vehicle to allow for possible loss to follow-up and the possibility that up to two clinical sites need to close due to COVID-19 before completion of the study. This sample size is based primarily upon safety considerations and is designed to ensure a minimum of 300 subjects treated with TP-03, 0.25%, for 43 days across two pivotal studies. Based upon prior clinical studies conducted in Mexico City and the previous Phase 2b/3 (Saturn-1) in the US with TP-03, 0.25%, for the treatment of *Demodex* blepharitis, this Phase 3 study should be adequately powered to demonstrate a difference between TP-03, 0.25%, and vehicle treatment arms.

Treatment assignment will be randomly assigned to reduce bias and the treatment assignment will be double-masked, unknown to the study participant, investigators and site staff performing study assessments.

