## 6.3 PARTICIPANT ID ASSIGNMENT AND MEASURES TO MINIMIZE BIAS: RANDOMIZATION AND MASKING

A balanced (1:1) randomization will be used for this study. A computer-generated blocked randomization schedule will be generated by [REDACTED]. [REDACTED] will use the randomization schedule to package the study drug. The labelled study drug will be shipped to the US distribution center for distribution to the clinical sites.

[REDACTED]

[REDACTED]

[REDACTED]

[REDACTED]

[REDACTED]

If a potential study participant has provided written informed consent and met all eligibility criteria, the participant is considered eligible to participate. If the potential participant elects to participate in the study, they can continue with the Day 1 procedure or be scheduled to return for Day 1. At Day 1, they will be dispensed the next available study drug bottle from the current site inventory by the Interactive Response Technology (IRT) system [REDACTED], which uses block stratification by site. The participant will receive their assigned study drug at the completion of the Day 1 visit and the participant will be considered enrolled in the study. The participant will be assigned a unique identification number consisting of their site number followed by a hyphen and then the screening number.

Throughout the study, both the participant and site personnel performing study assessments will remain masked to the study medication. The active and vehicle control ophthalmic solutions will be indistinguishable in appearance and will be distributed in bottles identical in appearance.

Treatment assignments should only be unmasked if needed for proper care of the participant. Sites will be provided instructions on the procedure to be followed to unmask the treatment assignment for a participant. Inadvertent unmasking will be reported to the sponsor and IRB as required.

[REDACTED]

[REDACTED]

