Based on the results from TRS-009 (Saturn-1) with response rates of 67.9% in the TP-03 treatment group and 17.6% in the vehicle treatment group for *Demodex* eradication and 13.9% in the TP-03 treatment group and 1.0% in the vehicle treatment group for composite cure, a sample size of 300 subjects still provides greater than 99% power to demonstrate superiority of TP-03 to vehicle for each endpoint.

For erythema cure, a sample size of 300 subjects will provide 88% power to demonstrate superiority of TP-03 to vehicle at a one-sided significance level of 0.025 based on the results from TRS-009 (Saturn-1), response rate of 19.1% for TP-03 and 7.4% for vehicle.

The study will be considered a success and TP-03, 0.25% will be considered superior to vehicle in clinical cure if H_{01} is rejected in favor of H_{11} . With this sample size, the study will have > 95% power to claim success for clinical cure. A closed hierarchical testing structure will be used such that the analysis will first be performed for the primary efficacy endpoint. Only if the null hypothesis for the primary efficacy endpoint is rejected will analyses be performed for the three secondary efficacy endpoints using the Hochberg testing strategy. Additional details can be found in [Section 8.5](#). If in addition to success for clinical cure, the largest p-value among the secondary endpoints allows for rejection of the null hypothesis in favor of the alternative hypothesis at a significance level of 0.025 then the study will also claim superiority of TP-03, 0.25%, to vehicle for all secondary endpoints. If the study cannot reject the null hypothesis for the secondary endpoint with the largest p-value, the next largest p-value among the remaining two endpoints will be evaluated at a significance level of 0.0125. The study will claim superiority of TP-03, 0.25%, to vehicle for both remaining endpoints if the null hypothesis is rejected in favor of the alternative hypothesis. If the study cannot reject the null hypothesis, the remaining secondary endpoint will be evaluated at a significance level of 0.0083. If the null hypothesis is rejected in favor of the alternative, the study will be able to claim success for the remaining secondary endpoint.

Accounting for a 30% discontinuation, approximately 209 subjects per arm (approximately 418 total) will be randomized. The planned enrollment is much greater than typically planned to achieve 300 completed

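### Does the 30% discontinuation allowance need correcting, given that 418 randomized leaves 300 completers only up to about 28% loss?

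*Protocol*

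**What the plan says.** Protocol section 9.2 takes 150 per arm as the powered sample: "A total sample size of 300 subjects (150 subjects per arm) yields approximately 99% power to establish superiority of TP-03 to vehicle". The test is specified as "using Pearson chi-squared to test a 1-sided hypothesis with a significance level of 0.025". The same section then inflates for loss: "Accounting for a 30% discontinuation, approximately 209 subjects per arm (approximately 418 total) will be randomized". SAP section 5 repeats that sentence.

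Both documents make clear that the 300 are meant to be completers and that the margin is deliberately wide. In SAP section 5: "The planned enrollment is much greater than typically planned to achieve 300 completed" subjects, with COVID-19 and the possible loss of up to two sites given as the reason.

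Protocol section 4.1 gives the lower figure as a floor, "The sample size is planned to be a minimum of 300 participants", and the upper figure as a limit: "The plan is to enroll up to 418 subjects in a 1:1 ratio of active: vehicle to allow for possible loss to follow-up". The synopsis (Protocol section 1.1) has the same limit: "Up to 418 participants will be enrolled". Section 4.1 adds that the size rests mainly on safety: at least 300 subjects treated with TP-03 for 43 days, counted over two pivotal studies.

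**The concern.** Three linked figures (300 completers, 30% loss, 418 randomized) should satisfy one equation, and they do not. The usual inflation divides by one minus the loss, which gives 430 with equal arms. The sentence exists to tell a reader how much loss the design can absorb before it falls below 300 completers, and read literally it overstates that margin by about two percentage points. At a true 30% loss, the trial would miss by about seven subjects the 300 that Protocol section 4.1 calls a minimum. The same sentence stands in both documents, so the rule that the SAP takes precedence does not settle it.

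If the confirmatory test were run on completers and power were marginal, a shortfall in the inflation could leave the trial underpowered. That possibility is what needs checking.

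**Working it through.** **Inputs.** From Protocol section 9.2 and SAP section 5: 300 completers (150 per arm), 30% discontinuation, about 209 per arm (418 in total), one-sided 0.025. Allocation is 1:1 (Protocol section 6.3). Primary response rates are 80.0% vs 15.8% (prior study outside the US) and 44.0% vs 7.4% (Saturn-1). Saturn-1 rates for the secondary endpoints, from SAP section 5: eradication 67.9% vs 17.6%, composite cure 13.9% vs 1.0%, erythema cure 19.1% vs 7.4%.

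**Step 1: try to reproduce 418.**
- Standard inflation, N/(1 − d): 300/0.70 = 428.6. Per arm, 150/0.70 = 214.3, so 215 per arm and 430 in total.
- The common shortcut, N × (1 + d): 300 × 1.30 = 390.
- With d = 0.28: 150/0.72 = 208.3, so 209 per arm and 418 in total.

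Neither formula gives exactly 418 at 30%. The standard one comes close: 418 is 10.6 below 428.6 (2.5%) and 12 below 430 (2.8%). An allowance of 28% does give 209, but neither document states that figure, so it is a reconstruction.

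**Step 2: what 418 absorbs.**
- Loss that leaves 300: 1 − 300/418 = 28.2%.
- Completers at 30% loss: 418 × 0.70 = 292.6, or 209 × 0.70 = 146.3 per arm.
- Shortfall against 300: 7.4 subjects, or 3.7 per arm (2.5%).

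**Step 3: what the shortfall would cost in power if completers alone were analysed.** With n per arm, the pooled normal approximation is

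power = Φ{ [ (p₁ − p₂)√n − 1.96 √(2p̄(1 − p̄)) ] / √(p₁(1 − p₁) + p₂(1 − p₂)) }, where p̄ is the mean of p₁ and p₂.

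For the primary endpoint at Saturn-1 rates and n = 146, p̄ = 0.257 and the argument is (0.366 × 12.083 − 1.96 × 0.618)/0.561 = 5.72, so power exceeds 99.9%.

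| Endpoint (rates) | 150 per arm | 146 per arm |
|---|---|---|
| Primary (80.0% vs 15.8%) | >99.9% | >99.9% |
| Primary (44.0% vs 7.4%) | >99.9% | >99.9% |
| Eradication (67.9% vs 17.6%) | >99.9% | >99.9% |
| Composite (13.9% vs 1.0%) | 99.1% | 98.95% |
| Erythema (19.1% vs 7.4%) | 85.2% | 84.2% |

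Exact binomial power of the chi-squared test gives 99.8% at both sizes for composite cure, and 86.3% then 85.6% for erythema. The erythema loss is therefore 0.7 to 1.0 percentage point. SAP section 5 quotes 88% for erythema at 300 subjects. That differs from both methods here at the same sample size, so the difference is a separate matter from the discontinuation allowance.

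**Step 4: does the confirmatory analysis use completers?** It does not. The Full Analysis Set is all randomized subjects (Protocol section 9.3, SAP section 7.1). Missing Day 43 data are imputed as failure after withdrawal for lack of efficacy or adverse events, and otherwise by multiple imputation (Protocol section 9.4.2, SAP sections 2.6 and 13.1). The number with observed data directly limits only the observed-data analyses, such as Sensitivity Analyses III and IV (SAP sections 13.1.1.3 and 13.1.1.4).

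**The case for a change.** The best case for a correction has four parts. The word approximately is attached to 209 and 418, while the 30% carries no qualifier. The count 209 is not a round number; it is just what 28% gives after rounding up, which suggests the wrong percentage was typed. The result crosses a floor that Protocol section 4.1 states. And the repair is one figure in each document.

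The arithmetic stands, and nothing else printed in either document reconciles the three figures. It is also fair that the floor would be missed by about seven subjects if loss really reached 30%. The safety aim in section 4.1 is where completing treatment matters most directly: 30% loss would leave about 146 TP-03 completers, not 150. Whether the two studies together would still reach 300 depends on the number treated in Saturn-1, which the documents do not give.

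The objection does not carry further than that. Loss has to fall between 28.2% and 30% for the discrepancy to decide whether 300 is reached. Rewording the percentage would not add a single subject, because enrolment is governed by the limit of 418, which appears consistently in the synopsis, section 4.1 and section 9.2. Writing 28% would also attribute to the sponsor a planning assumption that it never stated. The allowance covers ordinary loss to follow-up and possible site closures together, without separate figures, so a precision of two percentage points means little.

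**Conclusion.** No change is needed. The stated 30% is a loose description of an allowance that works out at 28.2%. The discrepancy is about 7 completers in 300 at a true 30% loss. It leaves primary power above 99.9% and composite power at about 99%, and it lowers erythema power by at most about one percentage point. Those power effects arise only in an analysis of completers, which is not the confirmatory one.

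This rests on three assumptions: that the 300 are completers, as both documents say; that loss is equal in the two arms; and that the response rates in the documents are reasonable planning values. The primary conclusion is insensitive to the last, since it holds at both sets of rates. If the documents are reopened for other reasons, an editor may write about 28%, or keep 30% and note that it leaves about 293 completers. Enrolment, endpoints, tests, significance levels and analysis sets are the same either way.
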